10.4.2 Analysis of the Primary Endpoint: Feasibility

The proportion of patients in whom BCI is successfully completed will be estimated, along with its 95% exact confidence interval.

10.4.3 Analysis of the Primary Endpoint: Safety

Safety endpoints will be descriptive in nature, and any possible, probable, or definite adverse event will be counted only once for a given participant. Frequency and severity of all adverse events will be reported, both in the total study population and stratified by dose level.

Dose-limiting toxicities will be tabulated in the whole population and by dose level. Bleeding severity will be graded based on severity scale as described in Section 4.1.1 (Primary Study Endpoints: Feasibility and Safety). Pneumothoraces will be reported and described based on size, associated

CONFIDENTIAL

symptomatology and respiratory impairment, and need for chest tube placement. Length of time to perform BCI and length of time of fluoroscopy exposure during BCI will be reported in minutes. Other adverse events will be recorded and categorized as per the NCI Common Terminology Criteria for Adverse Events (CTCAE) (33).

The maximum tolerated dose (MTD) will be determined based on the dose escalation rules described below and in Section 6.1.1. The MTD is the dose at which fewer than 1 of 3 or at most 1 of 6 participants on that dose experience a DLT.

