4.2 Study Endpoints

4.2.1 Primary Study Endpoints: Feasibility and Safety

- Each patient will be classified as having successfully undergone BCI or not. Feasibility of BCI is defined as successfully performing BCI in at least 80% of patients in whom BCI is attempted. Successful performance of BCI will require identification of the target peripheral lung tumor by radial endobronchial ultrasound within 20 minutes followed by completed cryoablation of target tumor. The target tumor will have freeze-thaw cycles applied every one centimeter of the largest diameter. Additional BCI features will be described as follows:
 - a) Ability of radial endobronchial ultrasound to identify peripheral lung tumor
 - b) Length of time to perform BCI
 - c) Length of time of fluoroscopy exposure during BCI
- 2) Dose-limiting toxicities (DLT) will be used to guide the dose-escalation procedure and determine the maximum tolerated dose. A DLT is defined as any of the following occurring up to 7 days post-BCI:
 - Grade 2 or 3 bleeding, based on the following scale (34):
 - a) Grade 0: absence of bleeding
 - b) Grade 1: bleeding requiring suctioning to clear
 - c) Grade 2: bleeding requiring an endoscopic procedure (iced saline, 1:20,000 topical epinephrine, or bronchial occlusion)
 - d) Grade 3: severe bleeding (>100cc total volume). Severe bleeding will also be defined as bleeding which cannot be controlled endoscopically, requires ICU admission or interventional radiology/ surgical intervention, or results in respiratory or hemodynamic instability (34)
 - Pneumothorax necessitating tube thoracostomy; recorded features of pneumothorax to include:
 - a) size
 - b) associated symptomatology
 - c) respiratory impairment
 - d) need for chest tube placement
 - Any NCI CTCAE (33) grade 3, 4, or 5 adverse events, which may be possibly, probably, or definitely related to BCI

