8.4 Study Halting Rules

If 2 or more participants experience DLT at any dose level, then the prior dose will be determined to be the MTD and the study will be terminated. Participants already enrolled in the study will be followed post procedure as per protocol. The study will be terminated in the event of death, massive hemoptysis, or acute respiratory distress syndrome (ARDS).

Additionally, the study will be suspended when three grade 3 AEs determined to be "probably related.". The medical monitor will notify the investigators immediately when the third grade 3 event is reported and enrollment screens will stop accepting new study participants. The investigators will inform the DSMB members within 24 hours of this occurrence and will provide the DSMB with AE listing reports. The DSMB will convene an ad hoc meeting by teleconference or in writing as soon as possible. The DSMB will provide recommendations for proceeding or halting the study.

8.5 Safety Oversight:

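### Bleeding is graded on a procedural 0–3 scale and gets no CTCAE grade, so non-severe late hemoptysis has no grade and all the worst bleeds share one

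*Combined protocol and SAP*

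**What the plan says.** Section 10.4.3 sets up two grading systems. For bleeding it says "Bleeding severity will be graded based on severity scale as described in Section 4.1.1". There is no Section 4.1.1; the scale is in 4.2.1 and is repeated in 8.1. For the rest it says "Other adverse events will be recorded and categorized as per the NCI Common Terminology Criteria for Adverse Events". It also promises the frequency and severity of every adverse event, overall and by dose level, with no rule for combining the two systems.

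On the bleeding scale, grade 0 is no bleeding. The next grades are "Grade 1: bleeding requiring suctioning to clear" and "Grade 2: bleeding requiring an endoscopic procedure (iced saline, 1:20,000 topical epinephrine, or bronchial occlusion". The top grade is "Grade 3: severe bleeding (>100cc total volume"), which a further sentence extends to bleeding beyond endoscopic control, bleeding that needs ICU, radiological or surgical care, and bleeding that causes instability. There is no grade above 3.

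In 4.2.1 and 8.1 a DLT is, within 7 days, grade 2 or 3 bleeding, a pneumothorax needing a chest tube, or any related CTCAE event of grade 3, 4 or 5. Section 3.1 gives the CTCAE limb as grade 4 or 5 only. Section 8.4 says "the study will be suspended when three grade 3 AEs determined to be" probably related, and names no scale. Separately, it ends the study for death, massive hemoptysis or ARDS.

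**The concern.** Section 2.3.1 names bleeding and hemoptysis among the risks of the procedure, and bleeding comes first in the DLT definition. A scale built around what the bronchoscopist does suits the procedure itself. But the DLT window is 7 days, adverse events are also recorded at the Day 14 visit, and 8.2.4 extends collection beyond that.

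Three things are at stake:

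- **Severity reporting.** Late minor bleeds have no place on the scale, and serious ones cannot be told apart by grade.
- **The CTCAE limb of the DLT definition.** It needs a CTCAE grade, which 10.4.3 does not assign to bleeds.
- **The suspension count.** Grade 3 on the bleeding scale and grade 3 on CTCAE are different measures, and 8.4 does not say which it counts.

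**Working it through.** The plan gives no figure on this point, so the first check sets the sections against each other.

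| Bleeding event | Grade, 0–3 scale (4.2.1, 8.1) | CTCAE grade under 10.4.3 | Route to a DLT |
|---|---|---|---|
| Cleared by suction at bronchoscopy | 1 | none assigned | not the bleeding limb |
| Treated endoscopically, at the index or a repeat bronchoscopy | 2 | none assigned | bleeding limb |
| After discharge, 100 cc or less, no endoscopic, ICU, radiological or surgical care, stable | none: bleeding is present, so not 0, and the criteria for 1, 2 and 3 are not met | none assigned | CTCAE limb only, with no grade to apply |
| 101 cc, otherwise uncomplicated | 3 | none assigned | bleeding limb |
| Life-threatening or fatal | 3 | none assigned | bleeding limb; death or massive hemoptysis also ends the study |

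The third row is the gap at the bottom of the scale. The last two rows are the loss of resolution at the top. The third row also shows the DLT inconsistency. Take a bleed of 100 cc or less that leads to an ordinary ward readmission. Under 4.2.1 and 8.1 its status turns on whether it is CTCAE grade 3 or higher; under 3.1, on whether it is grade 4 or 5; and 10.4.3 gives it no CTCAE grade. The documents do not reproduce the CTCAE criteria, so its grade cannot be worked out here.

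**Suspension rule, illustration only.** Suppose 8.4 counts grade 3 on the bleeding scale. No rate for this procedure exists. I assume p = 2%, 5.2% or 12% per participant. The last two are cryobiopsy rates from Section 2.1: 5.2% is bleeding in a review of 300 procedures, and 12% is hemoptysis of at least 100 cc in a review of 25. All bleeds are taken as probably related.

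*Ceiling, 24 participants, ignoring DLT stopping:* P(3 or more) = 1 − (1−p)^24 − 24p(1−p)^23 − 276p²(1−p)^22.

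- 2%: 0.012
- 5.2%: 0.126
- 12%: 1 − 0.0465 − 0.1522 − 0.2387 = 0.563

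*With DLT stopping.* Each such bleed is itself a DLT, and two at one level end the study. Bleeding alone therefore takes the count to three at a third level only if two earlier levels each had one bleed in six and the third has at least one in its first three. Let a = (1−p)³ (no bleed in three) and b = 3p(1−p)⁵ (one in the first three, none in the next three). Within 24 participants up to three clean levels can come in between (12 + 9 + 3 = 24), so P = b²(1−a)(1 + 3a + 6a² + 10a³).

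- 2%: a = 0.9412, b = 0.0542, bracketed sum 17.48; P = 0.003
- 5.2%: a = 0.8520, b = 0.1194, sum 14.10; P = 0.030
- 12%: a = 0.6815, b = 0.1900, sum 9.00; P = 0.103

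This assumes a standard 3+3, the same rate at every level and no other DLTs. Other grade 3 events would add to the count. If 8.4 means CTCAE grade 3, the contribution of bleeding cannot be computed from the documents.

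**The case against.** The case against is strong on safety capture. The 0–3 scale is a cited, procedure-specific scale. Its grade 3 criteria (volume, level of care, instability) apply after discharge as well as in the bronchoscopy suite, and a bleed treated at a repeat bronchoscopy within 7 days is grade 2. The CTCAE limb in 4.2.1 and 8.1 covers any related event and does not exclude bleeding. Section 10.4.3 is about reporting and does not redefine a DLT. Death or massive hemoptysis ends the study whatever the grade, 8.1.2 classes fatal and life-threatening events as serious, and 8.3.1 sends unexpected ones to the DSMB and IRB within 2 working days.

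All of that stands, and it rules out several stronger readings that a reader might infer:

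- *Hemoptysis after discharge cannot be graded at all.* Only non-severe hemoptysis lacks a grade.
- *Life-threatening or fatal bleeds escape the safety rules.* They do not; they merely share a grade with lesser bleeds.
- *An ungraded bleed would change an escalation step.* By definition that bleed is below grade 3 on the scale and had no endoscopic treatment. If it were related and CTCAE grade 3 or above, the limb in 4.2.1 and 8.1 would already make it a DLT. The documents show no bleed that ought to count and is lost.
- *The background bleeding rates show how often bleeds go ungraded.* They do not. The 12% rate is for bleeds of at least 100 cc, which is essentially the grade 3 threshold. The 4% rate after central-airway cryotherapy is for hemoptysis of unstated severity.
- *The plan prescribes pooling the two scales.* It does not; it leaves the matter open.

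Section 8.2.1 offers mild, moderate and severe for events outside the protocol's grading system, and a late minor hemoptysis could be read as falling there. That is arguable, because bleeding is in the protocol's system. It would also bring a third scale into the same table. Nothing in the objection supplies a CTCAE grade for bleeds or names the scale in 8.4.

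**Conclusion.** The point holds as a reporting and consistency defect in the primary safety analysis. One class of late, non-severe bleed has no grade on the protocol scale, and one grade covers everything from just over 100 cc to death. The CTCAE limb of the DLT definition applies to bleeds that 10.4.3 never grades on CTCAE, and the suspension rule can be read on either scale.

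For the suspension count, the illustration gives about 0.3% to 10% that bleeding alone brings the count to three at a third level when DLT stopping is respected. The ceiling without DLT stopping is 1% to 56%. These figures rest on assumed rates of 2% to 12%, partly borrowed from cryobiopsy, which the protocol itself distinguishes from this procedure. They show that the choice of scale can matter, not how often it will. The frequency of ungraded late bleeds cannot be estimated from the documents, and no effect on escalation or on the MTD has been shown.

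**What to change.** - In 10.4.3, also give every bleeding event a CTCAE grade at its worst severity, and use that grade in the all-event severity tables, overall and by dose level. Keep the 0–3 scale for the procedural bleeding table and for the bleeding limb of the DLT definition. Point the cross-reference to 4.2.1.
- In 8.4, state which scale grade 3 refers to.
- Reconcile 3.1 (CTCAE grade 4 or 5), 4.2.1 and 8.1 (grade 3, 4 or 5) and 10.4.3, so that one text says how a bleed enters the CTCAE limb. Which threshold applies is for the sponsor and investigators to settle.

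The cost is one extra CRF field per bleeding event and the wording changes. No additional participants, visits or procedures are needed.

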2.2.3 BCI Dose Rationale

BCI of peripheral lung tumors has not been performed previously. To maximize safety, the initial freeze time is shorter than standard freeze times for cryobiopsy of peripheral lesions (15). Our dose escalation will initiate patients at a safe freeze time for which there is extensive clinical experience with related procedures. If there is no complication from this, in the next cohort of patients we will gradually escalate dose to those higher than are routinely performed in bronchoscopic cryobiopsy.

CONFIDENTIAL

Freeze times will be escalated up to 30 seconds based on tolerability. In comparison, freeze times of up to 20 minutes have been safely administered during percutaneous cryoablation of peripheral lung tumors (7, 10). Although an optimal freeze time duration is unknown, longer freeze times may be needed in order to induce anti-tumor immune responses. Based on tolerability, freeze times will be increased as described in the following table:

| Dose Level | Freeze Time (per site) | Thaw Time |
|------------|------------------------|---|
| Level 1 | 1 second | Will last until the probe separates from target |
| | | tissue* |
| Level 2 | 2 seconds | Will last until the probe separates from target |
| | | tissue* |
| Level 3 | 3 seconds | Will last until the probe separates from target |
| | | tissue* |
| Level 4 | 5 seconds | Will last until the probe separates from target |
| | | tissue* |
| Level 5 | 10 seconds | Will last until the probe separates from target |
| | | tissue* |
| Level 6 | 20 seconds | Will last until the probe separates from target |
| | | tissue* |
| Level 7 | 30 seconds | Will last until the probe separates from target |
| | | tissue* |

* Thaw times at each dose level will be captured for each site.

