3.1 Primary Objective: Demonstrate Feasibility and Determine the MTD

1) Demonstrate feasibility of BCI

We hypothesize that BCI will be feasible, defined as successful performance in at least 80% of patients in whom BCI is attempted. Successful performance of BCI will require identification of the target peripheral lung tumor by radial endobronchial ultrasound within 20 minutes followed by completed cryoablation of target tumor.

2) Determine the safety and MTD of BCI

We hypothesize that BCI will prove safe at each planned dose level. Using a standard 3+3 design, the trial will determine the maximally tolerated dose (MTD) by sequentially assessing increasing freeze times during the procedure. Dose-limiting toxicity (DLT) is defined as the occurrence of any of the following: grade 2 or 3 bleeding, pneumothorax necessitating tube thoracostomy, or any NCI CTCAE grade 4 or 5 adverse events, which may be possibly, probably, or definitely related to BCI (33). The monitoring period for dose limiting toxicity will be for seven days post-BCI.

3.2 Secondary Objectives: Assess BCI Induced Anti-Tumor Immune Responses1) Pre- and Post-BCI Peripheral Blood Analysis

We hypothesize that BCI will induce activation and proliferation of peripheral blood T cells. Based on previous work (26, 27) (see section 2.1.IV for full details), we hypothesize that some combination of the following markers will be displayed on peripheral blood CD8⁺ T cells after BCI: HLA-DR and CD38 (surface markers of CD8⁺ T cell activation), Ki-67 (a cell cycle marker of proliferation), Bcl-2 (an anti-apoptotic protein downregulated on activated CD8⁺ T cells), and PD-1. We also hypothesize that there will be significant changes in peripheral blood lymphocyte gene expression after BCI, which will be assessed by the PanCancer OncoImmune[™] profile panel, a 770-plex gene expression panel covering innate and adaptive immune responses (NanoString® Technology, Seattle, WA).

2) Investigate BCI Association with PD-1 Phenotype of Effector T cells in NSCLC

We hypothesize that BCI will induce PD-1 phenotype in circulating effector T cells on single-cell RNA sequence analysis and that CD8+ T cell responses to BCI will be greater among subjects with high PD1 expressing T cells in BAL effluent.

4 Study Design and Endpoints

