6.1.2 Dose Escalation Protocol

A standard 3+3 dose escalation strategy will be used. The table below shows the doses that will be provided. Three participants will be initially enrolled at Level 1. If none of the first three participants at a given dose experiences dose-limiting toxicity (DLT), the dose will be escalated. If two or more of the first three participants experience DLT, the prior dose will be deemed the maximum tolerated dose (MTD) and the study will be terminated. If one of the first three participants experiences DLT, an additional three participants will be enrolled at the same dose. If among these six, only one experiences DLT, the dose will be terminated. If two or more of six experience DLT, the prior dose will be deemed the MTD and the study will be terminated. If the MTD is reached and only three participants have been treated at that dose, an additional three will be treated to ensure six subjects are treated at the MTD. DLT are defined in Section 4.1.1 (Primary Study Endpoints: Feasibility and Safety).

| Dose Level | Freeze Time (per site) | Thaw Time |
|------------|------------------------|---|
| Level 1 | 1 second | Will last until the probe separates from target tissue* |
| Level 2 | 2 seconds | Will last until the probe separates from target tissue* |
| Level 3 | 3 seconds | Will last until the probe separates from target tissue* |
| Level 4 | 5 seconds | Will last until the probe separates from target tissue* |
| Level 5 | 10 seconds | Will last until the probe separates from target tissue* |
| Level 6 | 20 seconds | Will last until the probe separates from target tissue* |

CONFIDENTIAL

| Level 7 | 30 seconds | Will last until the probe separates from target |
|---------|------------|---|
| | | tissue* |

6.1.3 **Procedures for Training of Clinicians on Procedural Intervention**

The NYU Interventional Pulmonary service has extensive experience using the flexible cryoprobe for debulking of central airway tumors. BCI will be performed by a board-certified, NYU Interventional Pulmonologist.

Only patients with the presence of a bronchus or airway path leading directly to the peripheral lung tumor will be eligible to undergo BCI. The peripheral tumor will also need to be identified by radial EBUS prior to performing BCI. If the peripheral tumor is unable to be identified by radial ultrasound within 20 minutes, then the patient will not be a candidate to undergo BCI.

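### If Level 7 (30 seconds) is cleared, the plan's definition labels it the MTD although no toxicity limit was found

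*Combined protocol and SAP*

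**What the plan says.** Section 10.4.3 states that the MTD follows from the dose escalation rules (it points to 6.1.1, but the rules stand in 6.1.2) and then adds: "The MTD is the dose at which fewer than 1 of 3 or at most 1 of 6 participants on that dose experience a DLT".

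The rules name an MTD in one way only. Section 6.1.2: "If two or more of six experience DLT, the prior dose will be deemed the MTD and the study will be terminated", with the same consequence for two or more DLTs among the first three. Section 8.4: "If 2 or more participants experience DLT at any dose level, then the prior dose will be determined to be the MTD". Section 6.1.2 also fixes the number treated at the MTD: "If the MTD is reached and only three participants have been treated at that dose, an additional three will be treated".

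The range is closed at the top. Section 2.2.3: "Freeze times will be escalated up to 30 seconds based on tolerability". The tables in 2.2.3 and 6.1.2 end at Level 7, 30 seconds. Section 3.1 states the expected outcome: "We hypothesize that BCI will prove safe at each planned dose level". Determining the MTD is part of the same primary objective, and 10.4.1 says that the study is designed to do so.

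**The concern.** An MTD claim has two parts: a dose was tolerated, and the next dose up was not. The rules in 6.1.2 and 8.4 require both. The count definition in 10.4.3 requires only the first. The two agree whenever some level fails above a cleared one. They part when nothing fails, because no dose lies above Level 7 for the rules to act on.

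In that case a primary result would say that a toxicity limit was located, when the data show only that the planned range was tolerated in three or six people at the top. Section 10.5 says that the results will inform the design of further BCI studies. A reader of those results could take 30 seconds as a ceiling, although the cap was set in advance and no toxicity set it.

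**Working it through.** **What each rule returns when Level 7 is cleared**

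| Rule | Condition for naming an MTD | Result at Level 7 |
|---|---|---|
| 6.1.2, 8.4 | two or more DLTs at the next dose up | none: there is no next dose |
| 6.1.2, 0 of 3 | escalate | cannot be carried out |
| 10.4.3 | 0 of 3, or at most 1 of 6 | Level 7 qualifies |

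Every cleared lower level also meets the 10.4.3 counts. Reading 'maximum' as the highest such dose still gives Level 7.

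**Reproducing the plan's table (10.5)**

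For a true DLT rate p, a level is cleared with 0 of 3, or with 1 of 3 followed by 0 of 3:

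f(p) = (1−p)^3 + 3p(1−p)^2 × (1−p)^3 = (1−p)^3 + 3p(1−p)^5

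At 10% to 70% this gives 0.906, 0.709, 0.494, 0.309, 0.172, 0.082 and 0.032, against the printed 0.91, 0.71, 0.49, 0.31, 0.17, 0.08 and 0.03. At 80% the formula gives 0.009 where the table prints <0.001; that cell plays no part here. The match shows that 1 of 6 counts as escalation, although the wording of 6.1.2 for 1 of 6 does not say so.

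**Chance that all seven levels clear**

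The DLT rates are assumed. The other halting rules in 8.4 are ignored.

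| Assumed flat rate | f(p) | f(p)^7 |
|---|---|---|
| 2% | 0.9954 | 0.968 |
| 5% | 0.9734 | 0.828 |
| 10% | 0.9061 | 0.502 |
| 20% | 0.7086 | 0.090 |

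With rates rising over Levels 1 to 7 as 1, 2, 5, 10, 15, 20 and 30%:

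0.9988 × 0.9954 × 0.9734 × 0.9061 × 0.8138 × 0.7086 × 0.4943 = 0.250

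These figures are for clearance before any expansion of Level 7 to six. If a Level 7 cleared on 0 of 3 is expanded and must end with at most 1 of 6, its factor becomes (1−p)^6 + 6p(1−p)^5, that is 0.9943, 0.9672 and 0.8857 at 2%, 5% and 10%, and 0.4202 at 30%. Multiplying by the chance of clearing Levels 1 to 6 gives 0.967, 0.823 and 0.490 for the flat rates and 0.506 × 0.4202 = 0.21 for the rising ones. The picture does not change.

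**What a cleared Level 7 establishes**

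Exact (Clopper-Pearson) two-sided 95% upper limits for the Level 7 DLT rate, where for zero events in n the limit is 1 − 0.025^(1/n):

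- 0 of 3: 1 − 0.025^(1/3) = 0.71
- 0 of 6: 1 − 0.025^(1/6) = 0.46
- 1 of 6: 0.64 (lower limit 0.004)

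**Number of participants**

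With no DLT at any level the path uses 7 × 3 = 21, and 24 once Level 7 is expanded by three. This equals the target of about 24 in 10.5 and the ceiling in the Protocol Summary.

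**The case against.** The strongest reply is that 10.4.3 should be read whole. Its lead-in makes the escalation rules govern, so the count sentence only describes the tolerability threshold, and those rules would never name Level 7. A reader might otherwise infer that 10.4.3 sets the escalation rules aside; it does not. But the rules it defers to return nothing for a cleared Level 7, so the count sentence is the only text left that yields a result, and it yields 30 seconds.

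A second reply is that this is labelling within an openly capped range, and that DLTs are tabulated by dose level (10.1, 10.4.3), so a careful reader would see that no level exceeded the limit. That stands, and it bounds the harm. It does not make the headline of a primary objective correct.

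A third reply is that the probabilities rest on assumed rates. That also stands. A reader might want to fix the rate from the cryobiopsy complications cited in 2.1 (5.0% and 5.2%; 8% and 12%). The documents do not support that: those procedures remove tissue, all pneumothoraces are counted whereas only one needing a chest tube is a DLT, and adding the two rates assumes that no patient had both. Rates below those would make a cleared Level 7 more likely.

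**Conclusion.** The point holds for the top of the dose range. As written, the plan would report an MTD of 30 seconds in the outcome that it hypothesises, with no intolerable dose observed. Under the assumed rates that outcome has probability 0.97, 0.83 or 0.50 (flat 2%, 5%, 10%) or 0.25 (rising from 1% to 30%); it falls to 0.09 at a flat 20%.

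Two stronger readings are not supported. The first is that participants would be wrongly dosed or the trial wrongly continued: the escalation and DLT stopping thresholds are the same whichever label is used. The only operational loose end is whether a Level 7 cleared on 0 of 3 gets three more participants, since that depends on whether it is called the MTD. The second is that two or more DLTs at Level 1 would lead to a wrong dose being declared. The rules then point to a prior dose that does not exist, but the study stops and no dose can be misnamed. That is a missing detail, worth only a note.

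One limit applies: the study schematic is not shown, and an outcome for a cleared Level 7 could be stated there.

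**What to change.** In 10.4.3, define the MTD as the highest dose with at most 1 of 6 DLTs when the next higher dose had two or more DLTs. If Level 7 is cleared, report 'MTD not reached; highest freeze time tested 30 seconds', with the number treated and the exact 95% confidence interval for its DLT rate.

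In 6.1.2, say that the expansion to six also applies to a Level 7 cleared on 0 of 3. Without this sentence the new definition would remove the label that triggers the expansion, and the upper limit with no DLTs would be 71% instead of 46%.

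As a minor addition in 6.1.2 and 8.4, report two or more DLTs at Level 1 as 'no planned freeze time tolerated; MTD not established'.

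The cost is a few sentences and the chance that the headline reads 'MTD not reached'. No escalation or DLT stopping threshold changes. Expanding Level 7 fits 24 participants when no lower level was expanded; each lower level that was expanded adds three. If the added three bring Level 7 to two or more DLTs, Level 6 becomes the MTD and may itself need three more.
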